6.4 Human Pharmacokinetics

Following pharmacokinetic (PK) data were obtained from a placebo-controlled, Phase I, single dose escalating and repeat-dose study in healthy volunteers and a Phase IIa study in patients with acute respiratory distress syndrome (ARDS). For further information please see Investigators brochure chapter 5 [6].

Placebo-controlled, Phase I, single dose escalating and repeat-dose study in healthy volunteers:

Systemic ACE2 enzymatic activity was measured in plasma, and this measure was used to describe the exposure of GSK2586881 (APN01). Determination of rhACE2 content in plasma samples using a “sandwich” enzyme-linked immunosorbent assay (ELISA) was also conducted and the results showed good correlation, and yield similar results up to about 10 µg/ml. There was however a slight difference at higher values, where the ELISA figures become smaller than ACE2 enzymatic activity, but the difference was relatively small with approximately 20 % lower at around 20 µg/ml range. The summary of systemic exposure of APN01 as measured by ACE2 enzymatic activity assay following single dose of APN01 from 0.1 mg/kg to 1.2 mg/kg, is shown in Table 2.

Table 2: Summary of systemic PK in healthy volunteers following single dose of GSK2586881 (APN01-1-01)

Cohort	1	2	3	4	7
Dose	0.1mg/k	0.2mg/	0.4mg/k	0.8mg/k	1.2mg/k
N	3	3	3	3	3
	AUC¹				
Geometric (GEO) Mean	17.27	26.60	67.84	81.80	141.70
CI 95% Lower GEO Mean	7.84	17.41	53.81	57.45	75.55
CI 95% Upper GEO Mean	38.04	40.65	85.52	116.48	265.78
	C_{max}²				
Geometric Mean	2.01	2.85	6.30	12.72	21.03
CI 95% Lower GEO Mean	1.42	1.85	5.58	7.00	16.76
CI 95% Upper GEO Mean	2.86	4.39	7.12	23.13	26.40

1. Area under the curve (AUC) for each subject was taken from Apeiron APN01CSR (Apeiron Biologics AG) and summarized in house
2. C_{max} was calculated and summarized in house from raw data; Note: C_{max} was not reported in Apeiron APN01 CSR

Systemic exposure of GSK2586881 appeared to increase with increasing dose, and the increase was approximately dose proportional. GSK2586881 cleared quickly from systemic, with median clearance of 589 mL/h and median half-life of 9.8 hours.

Exploration of PK profiles indicated that GSK2586881 showed a bi-exponential decline, with an initial quick distribution phase followed by a relatively slower elimination phase.

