8.4.7 Prior and Concomitant Therapy

Prohibited treatment: Patients receiving ACE inhibitors, or renin inhibitors

NOTE: angiotensin receptor blockers are not prohibited.

Concomitant treatment: Any concomitant treatment given for any reason during the course of the study must be recorded on the eCRF and in the patient’s medical records, including dosage, start and stop dates and reason for use.

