8.7.2 Determination of Sample Size

186 patients (93 per group) will yield 80% power to detect a 20% absolute risk reduction in the primary composite endpoint, from 50% in the placebo group to 30% in the APN01 group at a two-sided alpha of 0.05 when applying a two group Chi-Squares test. To consider patients who will be randomized but not treated a total of 200 patients (100 per group) will be enrolled.

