9.1 Protocol Deviations

All protocol deviations will be tracked and actions will be defined, as feasible. All protocol deviations will be reviewed and classified in the DRM before data base lock and unblinding for the final analysis for assessment of their influence on the quality of the study analysis.

Protocol deviations (PD) are defined as follows:

Major PD:

- Informed consent procedure: ICF not signed and dated by patient/investigator
- Violation of an in- or exclusion criterion
- Randomization procedure
- Incorrect use of IMP (storage, preparation and administration)
- Use of forbidden concomitant medication
- Delayed reporting of serious adverse events

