3.3 Per-Protocol Analysis Set (PP)

The PP includes all subjects included in the SAF who had no major protocol deviations and completed through Day 28 or until discharge from the hospital (end of study follow-up). Protocol deviations will be identified and classified for each subject during a blind data review meeting (BDRM) (see section 4.8).

The following protocol deviations are a priori defined to have a “major” grade and will lead to an exclusion from the PP set:

- ❑ Informed consent procedure: ICF not signed and dated by patient/investigator
- ❑ Violation of an in- or exclusion criterion
- ❑ Randomization procedure
- ❑ Incorrect use of IMP (storage, preparation and administration)
- ❑ Use of forbidden concomitant medication
- ❑ Delayed reporting of serious adverse events

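### The per-protocol set excludes patients for late SAE reporting, a site failure that can occur only after an SAE, so the set is partly selected on post-randomization outcome (minor).

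*SAP*

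**What the plan says.** SAP 3.3 takes the PP set from treated patients who completed follow-up and had no major deviation. It names six deviations as major in advance and states that each "will lead to an exclusion from the PP set". They cover consent, eligibility, the randomization procedure, handling and administration of study drug, forbidden medication, and late SAE reporting. Protocol 9.1 has the same list, including "Delayed reporting of serious adverse events".

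Neither list defines lateness. The only deadline is in protocol 8.5.2.2.13.2.1: the investigator must report within 24 hours of becoming aware of the event. Protocol 8.5.2.2.13.2.2 counts any event after first dosing that results in death as an SAE. SAP 4.4.1 makes death one of the two components of the primary endpoint.

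On medication, protocol 8.4.7 says only "Prohibited treatment: Patients receiving ACE inhibitors, or renin inhibitors", with no stated end. The study schedule records concomitant medication to Day 28, and the definition in SAP 4.2 has no upper limit. Dosing ends on Day 7, or on the morning of Day 8 under SAP 4.3.

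SAP 3.4 bases all efficacy analyses on the FAS and repeats the main efficacy outcomes in the PP set.

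**The concern.** A PP set is meant to show the result in patients who were treated as planned. An exclusion belongs in it if it marks a departure in treatment, eligibility or conduct that could alter what the treatment did. Late SAE reporting does not. A patient who received all 14 doses correctly and then died leaves the PP set if the site reported the death late. A patient with no SAE can never leave by this route. The exclusion is thus tied by definition to what happened after randomization, and in part to the primary endpoint itself.

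The PP set is the only alternative analysis set for the main efficacy outcomes, so readers will compare it with the FAS. Part of any gap between the two could then come from site paperwork in patients who fared badly.

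The forbidden-medication rule raises a lesser question. As written, an ACE inhibitor started on, say, Day 20 after a full course of study drug also removes the patient.

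**Working it through.** **Inputs.** Protocol 8.7.2 gives the design: "186 patients (93 per group) will yield 80% power", "from 50% in the placebo group to 30% in the APN01 group", "at a two-sided alpha of 0.05 when applying a two group Chi-Squares test", and "a total of 200 patients (100 per group) will be enrolled". The documents give no deviation rates, so every exclusion share below is an assumption, ranging from 0 to 30%.

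**The plan's own figure.** With pooled variance and no continuity correction, n = [1.960 × √(2 × 0.4 × 0.6) + 0.842 × √(0.5 × 0.5 + 0.3 × 0.7)]² / 0.20² = 93 per group. Power at 93 per group is 80.0%, so the figure reproduces. At 100 per group it is 82.8%.

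**Effect of an outcome-linked exclusion.** Let p be the true event rate, and e and f the shares of event and non-event patients removed. The PP event rate is p(1−e) / [p(1−e) + (1−p)(1−f)].

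Late SAE reporting, with the same e in both arms, f = 0 and 100 randomized per arm:

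| e | Placebo | APN01 | Difference (points) | Odds ratio | Power |
|---|---|---|---|---|---|
| 0% | 50/100 = 50.0% | 30/100 = 30.0% | 20.0 | 2.33 | 82.8% |
| 10% | 45/95 = 47.4% | 27/97 = 27.8% | 19.5 | 2.33 | 80.3% |
| 20% | 40/90 = 44.4% | 24/94 = 25.5% | 18.9 | 2.33 | 77.2% |
| 30% | 35/85 = 41.2% | 21/91 = 23.1% | 18.1 | 2.33 | 73.4% |

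The odds ratio does not move because (1−e) multiplies the event odds in both arms and cancels. At 20%, (40/50)/(24/70) = 2.33, the same as (50/50)/(30/70). For the same reason, equal true rates stay equal.

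**When a false difference appears.** The share removed must differ by arm within the same outcome. Take a true rate of 50% in both arms:

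- 10% of placebo events and 20% of APN01 events removed: 45/95 = 47.4% vs 40/90 = 44.4%, a false 2.9 points.
- 10% and 30% removed: 47.4% vs 35/85 = 41.2%, a false 6.2 points.

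**Forbidden medication, if it fell only on non-event patients.** Removing 10% of them in both arms gives 50/95 = 52.6% vs 30/93 = 32.3%, a difference of 20.4 points; the odds ratio is (50/45)/(30/63) = 2.33. Adding the 20% late-SAE case gives 40/85 = 47.1% vs 24/87 = 27.6%, or 19.5 points. The two rules push in opposite directions and partly cancel.

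**Exposure after the last dose.** Protocol 6.4 reports "median clearance of 589 mL/h and median half-life of 9.8 hours" in healthy volunteers, so five half-lives are 5 × 9.8 = 49 h. The ARDS population model in the same section (V = 5.79 L, CL = 0.384 and 0.698 L/h) gives half-lives of ln2 × 5.79/0.384 = 10.5 h and ln2 × 5.79/0.698 = 5.7 h, so five half-lives are about 29 to 52 h. Use that begins well after that is not concurrent exposure, although some exposure does outlast the final dose.

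**The case against.** The strongest reply is that little depends on this. The FAS is primary, and no test, alpha or sample size rests on the PP set. Investigators and patients are blinded and deviations are classified before unblinding, so nothing in the documents suggests that lateness would differ by arm. All of that stands, and it is why the point is minor. Blinding makes arm-dependent lateness unlikely, but it does not make a reporting lapse a measure of adherence. The classification also uses all data, and SAP 3.3 leaves no discretion over the listed items.

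A reader might infer more than the documents support:

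- *That the PP set is selected on outcome instead of adherence.* Four of the six exclusions (consent, eligibility, randomization, study drug) are not tied to outcome by definition, and forbidden medication during dosing is a proper adherence criterion.
- *That late SAE reporting removes only patients with primary events.* The SAE criteria include prolonged hospitalization and important medical events, which event-free patients can have. Invasive ventilation is not itself a listed criterion. The clock runs from the investigator's awareness, so having an event does not make its report late.
- *That a comparison of PP with FAS cannot be interpreted.* With shares equal across arms, the odds ratio and a true null are preserved, and the risk difference stays between 18.1 and 20.0 points over the assumed range.
- *That forbidden medication arises mainly in survivors.* They have longer to start such drugs, so it is plausible. But no rates are given, recent users are excluded at entry (exclusion criterion 21), and angiotensin receptor blockers are allowed.

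Where the medication window should end is also open. Stopping at the last dose would admit the residual exposure calculated above. Because APN01 acts on the renin-angiotensin system and the endpoint runs to Day 28, a longer window can be defended.

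**Conclusion.** The point holds for late SAE reporting, as a minor one. From the definitions alone, the rule can remove correctly treated patients who had an SAE, including any who died, and cannot remove a patient without one. No assumed rate is needed for that.

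The size does rest on assumptions. With equal lateness across arms, removing 20% of event patients turns 50% vs 30% into 44.4% vs 25.5%, leaves the odds ratio at 2.33, and lowers PP power from 82.8% to 77.2%. A spurious PP difference needs lateness that differs by arm, which the documents give no reason to expect. The primary result is not affected.

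On forbidden medication, the missing end date is a real gap in the definition of the PP set. Its link to outcome is unproven.

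**What to change.** Before unblinding:

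1. In SAP 3.3, remove late SAE reporting from the deviations that exclude a patient from the PP set. Keep it as a reported deviation under protocol 9.1 and in the blind data review.
2. In SAP 3.3, state the analysis window in which forbidden medication counts against PP membership. The sponsor should choose it blinded and give the reason. Use outside the window is listed. This defines an analysis set only and leaves the prohibition in protocol 8.4.7 as it is.
3. Record both changes in SAP section 5.

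The cost is a few lines of SAP text. No new data are needed, since medication and deviations are already collected, and the primary analysis does not change.

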3.4 Assignment of Analysis Sets to Analysis

The FAS serves as the primary efficacy analysis set (as randomized). All efficacy analyses are based on the FAS. The SAF will be used for the evaluation of the safety assessments (as treated) unless stated otherwise. All biomarker analyses are based on SAF (as treated) as well. The PP will only be analyzed for main efficacy outcome measures (as treated).

4 Statistical Evaluation

Continuous variables will be summarized with means, standard deviations, medians, lower and upper quartiles, minimums and maximums. Frequencies and percentages will be used to summarize categorical variables.

The two different treatment groups (groups APN01 and Placebo) will be separately tabulated. Where appropriate total columns will additionally be displayed for the two treatment groups combined.

A detailed description of the planned tables, listings and graphs is given in Appendix A.

Baseline

Baseline is defined as last observation before treatment, i.e. Day 1 value or Screening value if Day 1 value is missing or if Screening and Day 1 is the same day, unless stated otherwise.

Visit terminology

Visit No.	Notation used on the case report form	Notation used for tables, listings and graphs
10	Screening (Day -1)	Screening
150	Unscheduled visit	Screening *
20	Day 1	Day 1
30	Day 2	Day 2
40	Day 3	Day 3
50	Day 4	Day 4
60	Day 5	Day 5
70	Day 6	Day 6
80	Day 7	Day 7
150	Unscheduled visit	Day 8 *
90	FU Day 10	FU Day 10
100	FU Day 14	FU Day 14
110	FU Day 28/EOS	FU Day 28/EOS
130	FU Day 28/EOS Phone Visit	FU Day 28/EOS
170	Russia only: Home Visit FU Day 28/EOS	FU Day 28/EOS
120	Early termination	ET
140	Early termination FU Day 28/EOS	ET
150	Unscheduled visit	Unscheduled visit

ET = Early termination

** IMP administration at Screening and at Day 8 as well as all related assessments (e.g. ECG, Vital signs, etc.) are documented in eCRF as IMP administration or assessment on Unscheduled visit and will be shown in TLGs as IMP administration or assessment on Screening and Day 8 respectively.*

Unscheduled visits will not be included in any tables or graphs, only in listings and will be displayed after all scheduled visits.

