1 STUDY SCHEME

2 STUDY SCHEDULES

Table 1:

Procedures and assessments	Screening period	Treatment period ²⁰							Follow up period		
	Day -1*	Day 1	Day 2	Day 3	Day 4	Day 5	Day 6	Day 7	Day 10 (±1 day) ¹⁶	Day 14 (± 1 day) ¹⁶	Day 28 End of Study Visit (or early termination visit) (± 1 day) ¹⁵
Informed consent	X										
Inclusion and exclusion criteria	X	X ※**									
Demographics ¹	X										
Medical history ²	X										
Randomization*		X ※*									
Treatment		X ¹⁴	X	X	X	X	X	X			
Score Assessment of WHO's 11-point scale	X	X ※**	X	X	X	X	X	X	X	X	X ¹⁹
PCR (quantitative or qualitative) ³	X	X ※**		X		X		X		X	X ¹⁷
Vital signs ⁴	X	X ※	X	X	X	X	X	X	X	X	X ^{17, 18, 19}
Physical examination ⁵	X	X ※**	X	X	X	X	X	X	X	X	X ^{17, 19}
Serum or urine pregnancy test ⁶	X										X ^{17, 19}
Clinical laboratory assessments ⁷	X	X ※**	X	X		X		X	X	X	X ^{17, 19}

	Screening period	Treatment period ²⁰							Follow up period		
Procedures and assessments	Day -1*	Day 1	Day 2	Day 3	Day 4	Day 5	Day 6	Day 7	Day 10 (±1 day) ¹⁶	Day 14 (± 1 day) ¹⁶	Day 28 End of Study Visit (or early termination visit) (± 1 day) ¹⁵
HIV/HBV/HCV Serology ⁸	X										
ECG ⁹	X	X ※**	X	X		X		X	X	X	X ^{17, 19}
Assessment of Respiratory condition ¹⁰	X	X ※**	X	X	X	X	X	X	X	X	X ¹⁷
mSOFA score	X	X ※**	X	X	X	X	X	X	X	X	X ¹⁷
Assessment of Immune function ¹¹		X ※**	X	X		X		X	X	X	X ^{17, 19}
Biomarker ¹²		X ※		X		X		X		X	X ^{17, 19}
Patient status assessment ¹³			X	X	X	X	X	X	X	X	X ¹⁷
Adverse Events		X	X	X	X	X	X	X	X	X	X
Concomitant Medication		X	X	X	X	X	X	X	X	X	X

* In case the required screening procedures take less time, randomization and start of treatment could be performed also on the same day then screening. The time period between start of screening procedures and start of treatment must not exceed 24 hours.

** Events do not need to be done if randomization is on the same day as Screening

※: prior dosing

mSOFA score: modified Sequential Organ Failure Estimated Score

¹ Demographic data: gender, age, ethnicity, height, history of allergies, history of smoking and alcohol use, weight, body mass index.

² Medical history: Medical history for the least 4 weeks.

³ If PCR was performed within 5 days before the screening visit, the test does not need to be repeated at screening and the available test results can be used.

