1. Plasma-Renin-Concentration (PRC)
2. Cytokines: interleukin- 6 (IL-6), interleukin- 8 (IL-8), soluble tumor necrosis factor receptor II (sTNFrII), PAI-1, vWF, tumor necrosis factor - α
3. Alveolar epithelial markers: soluble advanced glycation product receptor (sRAGE), surface-active protein- D (SP-D)
4. endothelial markers: angiopoietin -2 (Angiopoietin-2)
- 5.
6. COVID-19 antibodies, viral load

¹³ Patient status assessments includes: no change, discharge from hospital, transition to critical illness, and death.

¹⁴ 1st dosing could also be on the evening of Day -1 in case randomization is on the same day as screening.

¹⁵ Follow-up Visits (Day 28) may be performed as phone visit or in-home visit where applicable. .

¹⁶ If a patient is already discharged from the hospital, the follow-up visits could be performed on an out-patient basis or at patient's home provided the patient agrees to that.

¹⁷ Assessments do not have to be performed in case of a phone visit

¹⁸ Targeted Physical examination by phone interview

¹⁹ The following assessments will be performed during in home-visits (Clinical Laboratory assessment, ECG, Assessment of immune function and Biomarker, if possible)

²⁰ If a patient will be discharged from hospital before day 7 treatment can be stopped at day of discharge.

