8.4 Treatments

8.4.1 Treatments Administered

8.4.1.1 Experimental Intervention

Administration of APN01 (on top of SOC) will be carried out according to investigators brochure (IB) and Pharmacy Manual. Dosing will be 0.4mg/kg twice a day (BID), administered for seven days, every 12 hours (\pm 1 hour). First dosing could either be in the morning of Day 1 or in the evening of Day -1. If a patient will be discharged before day 7, treatment can be stopped early at day of discharge.

The IMP should only be administered if the staff, trained to evaluate and manage anaphylactic reactions, is immediately available, and in an environment where full resuscitation facilities can be assured. Each patient should be observed for adverse effects following APN01 administration. If hypersensitivity reactions or signs of intolerance occur during administration, the treatment must be stopped immediately. Facilities for cardio-respiratory resuscitation and equipment for handling acute anaphylactic/ anaphylactoid reactions should be available. Additional treatment with antihistamines and/or corticosteroids should be given as appropriate.

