3. Ventilator-free days (VFD) up to 28 days or hospital discharge

VFD will be analyzed for both all patients as well as for the subgroup of patients who were alive at Day 28 or hospital discharge. For the analysis of all patients separate analyses will be conducted for patients who died: a) VFD will be set to 0, b) the observed VFD until death will be considered. Summary tables will be generated the VFD will be compared using Wilcoxon rank sum test. In addition, bootstrap methods will be applied to calculate 95% confidence intervals and two-sided p-values for the difference in means.

4. Proportion of responders, defined as ≥ 2 improvement in WHO's 11-Point Score system at day 7, 10, 14 and 28

Similar analyses as for 28-day mortality will be conducted.

5. Time to death (all cause) will be analyzed using Kaplan-Meier estimates and plots, log-rank test, and Cox proportional hazards model (adjusted for minimization factors to derive hazard ratios and corresponding 95% confidence intervals). Patients who will be alive at Day 28, or who will be discharged from hospital before day 28 with no information on death until day 28, will be censored at discharge if they cannot be reached at or after day 28 by means of a telephone interview. Further details will be described in the statistical analysis plan.

6. Proportion of patients with any use of invasive mechanical ventilation up to 28 days or hospital discharge

Similar analyses as for 28-day mortality will be conducted.

7. Time to first use of invasive mechanical ventilation up to 28 days or hospital discharge
Similar analyses as for time to death will be conducted. Patients without invasive mechanical ventilation will be censored on the last day of evaluation. For patients who died the observed time to first use of invasive mechanical ventilation will be considered; if a patient who died did not receive any mechanical ventilation, the patient will be censored on time of death.

8. Absolute values and absolute change in P/F ratio over time

The PF ratio is defined as PaO₂ [mmHg] divided by FiO₂ in [%] and will be evaluated on each visit. Summary statistics for the PF ratio for both the absolute values and the absolute change from Baseline (day 1) will be tabulated.

9. Absolute values and absolute change in the modified Sequential organ failure assessment score (mSOFA score) over time

Similar analyses as for the PF ratio will be conducted.

10. Time to a 2-point decrease in WHO scoring scheme.

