4.3 Study Drug Administration

IMP administration

Each patient should receive 14 doses of IMP (APN01 or Placebo). The first IMP administration will be performed after randomization at screening or at day 1. If the first IMP administration is performed at day 1 at the evening, patient will receive the 14th dose on day 8 in the morning. IMP administration at screening and at day 8 as well as all related assessments (e.g. ECG, Vital signs, etc.) are documented in eCRF as IMP administration or assessment on unscheduled visit and will be shown in TLGs as IMP administration or assessment on screening and day 8 respectively (instead of unscheduled visit, i.e. renaming of unscheduled visits in this cases).

Total study drug exposure and total study drug exposure complete will be tabulated and listed.

Therefore, the frequency tables in overall as well as by Age group (< 65 years/ >= 65 years to < 75 years/ >= 75 years to < 80 years/ >= 80 years), Sex, Race and Ethnicity will be provided.

Total study drug exposure [days] is calculated as sum of days with at least 1 administered dose (complete or not complete) of IMP (APN01 or Placebo).

Total study drug exposure complete [days] is calculated as sum of days with two complete administered doses of IMP (APN01 or Placebo).

All other IMP administration data will be listed only.

Total dose per day of study medication taken [mg] is calculated as sum of first and second administered doses of IMP (APN01 or Placebo).

Total volume per day of infusion [ml] is calculated as sum of first and second administered volume of infusion.

Total dose of study medication taken [mg] is calculated as sum of daily administered doses of IMP (APN01 or Placebo).

Total volume of infusion [ml] is calculated as sum of daily administered volume of infusion.

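### The SAP's baseline rule goes by visit label, so a value taken after an evening Day -1 first dose can be selected as baseline

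*SAP*

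**What the plan says.** SAP section 4, Baseline, opens with a principle and then applies it by visit: "Baseline is defined as last observation before treatment, i.e. Day 1 value or Screening value if Day 1 value is missing". The same sentence adds a second case in which Screening replaces Day 1: "or if Screening and Day 1 is the same day, unless stated otherwise".

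The first dose is not tied to Day 1. Protocol 8.4.1.1 says: "First dosing could either be in the morning of Day 1 or in the evening of Day -1". Table 1, footnote 14, gives the condition: "1st dosing could also be on the evening of Day -1 in case randomization is on the same day as screening". SAP 4.3 agrees: "The first IMP administration will be performed after randomization at screening or at day 1". SAP 4.4 also plans for a first dose on the night of Screening, by widening the Day 28 window.

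For same-day randomization, Table 1 relaxes the double-starred Day 1 items, which include clinical laboratory tests (LDH among them), WHO score and mSOFA: "Events do not need to be done if randomization is on the same day as Screening". Protocol 8.5.2.1 keeps biomarker sampling and vital signs outside that waiver, and 8.5.2.2 requires Day -1/1 assessments before dosing.

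Two variables have their own baseline. Vital signs use the Screening value (SAP 4.5), and PaO2/FiO2 uses its first observed value (SAP 4.4.2). For several secondary endpoints the protocol equates baseline with Day 1: "the absolute change from Baseline (day 1) will be tabulated" (Protocol 8.7.1.2.5).

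**The concern.** The two halves of the SAP sentence agree only if nobody is dosed before Day 1. For a patient dosed on the evening of Day -1, a value recorded the next morning satisfies the label but breaks the principle, and the SAP does not say which half a programmer should follow.

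A baseline taken after the first dose can carry an early drug effect in the APN01 arm only. Three kinds of output depend on it:

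- Change-from-baseline tables for laboratory values, mSOFA and biomarkers, and those for vital signs through the separate Screening rule.
- The Day 5 log-LDH regression, labelled the powered secondary endpoint, where baseline log-LDH is a covariate. A covariate measured after treatment can absorb part of the effect being estimated.
- The 2-point WHO improvement and the time to it. SAP 4.4.2 names no starting score, so I assume the general baseline applies.

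**Working it through.** The plan gives no figure on this point. The sample size of 186 rests on a binary endpoint with no baseline value, so it is not involved. The check is to run the literal rule through the permitted cases.

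| First dose | Value on file | Rule selects | Before first dose? |
|---|---|---|---|
| Day 1, Screening the day before | Day 1, taken before dosing | Day 1 | Yes |
| Day 1, Screening the same day | Screening | Screening | Yes |
| Evening of Day -1 | Day 1 item waived and not done | Screening | Yes |
| Evening of Day -1 | Day 1 laboratory, WHO or mSOFA done anyway | Day 1 | **No** |
| Evening of Day -1 | Biomarker drawn before that dose, filed as Day 1 | Day 1 | Yes |
| Evening of Day -1 | Biomarker drawn only before the Day 1 morning dose | Day 1 | **No** |

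**Row 4.** The waiver makes these tests optional; it does not bar them. The same-day exception does not help, because Day 1 is then the following day. SAP section 4 and 4.3 treat a dose at Screening as a separate event, documented as an unscheduled visit and displayed as Screening.

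**Row 6.** Table 1 has no Day -1 cell for biomarkers, only a Day 1 cell marked as before dosing. A sample taken before the second dose fits that mark, yet follows the first. Protocol 8.5.2.1 points to a true pre-dose sample, but the SAP rule is not tied to it.

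**Vital signs.** Readings are due before and after each dose (Table 1, footnote 4). Those around a Day -1 dose are displayed as Screening (SAP section 4 and 4.3), and baseline is the Screening value (SAP 4.5). Nothing excludes the post-dose reading.

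**Size.** For LDH, CRP, D-dimer, mSOFA and WHO score, the documents give no effect about 12 hours after one dose, so nothing can be computed. Plasma ACE2 activity, used in Protocol 6.4 as the measure of drug exposure, allows an illustration for one affected patient. Assume simple first-order decline and 12-hour dosing.

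- Fraction left after 12 h: r = 2^(-12/half-life). At 9.6 h (Protocol 8.4.5), r = 0.420. At 9.8 h (Protocol 6.4), r = 0.428.
- The ARDS Part B estimates in Protocol Table 3 give a half-life of 0.693 × 5.79 / 0.698 = 5.75 h, so r = 0.235.
- Later trough, in units of one dose's rise: r/(1 - r). Measured from a baseline already raised by r, the change is r/(1 - r) - r = r²/(1 - r).
- Ratio of shown to true change: [r²/(1 - r)] / [r/(1 - r)] = r, that is 42 to 43%, or about 24% with the ARDS estimates.
- If a share f of APN01 patients has a post-dose baseline and true changes are equal, the mean rise is understated by f(1 - r). Assumed shares of 10%, 25% and 50% give about 6%, 14% and 29%, or 8%, 19% and 38% with the ARDS estimates. The documents give no f, and it may be zero.

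**The case against.** The strongest reply is that the SAP already has the right rule. Its opening words exclude any post-dose value, and the visit labels after them can be read as illustration. Dosing on Day -1 requires randomization on the screening day, which is exactly when the double-starred Day 1 items are waived; a site using the waiver has no Day 1 value, and Screening is correctly used. Protocol 8.5.2.1 and 8.5.2.2 call for a pre-dose biomarker sample, and a compliant sample filed under Day 1 is the right baseline. The primary endpoint uses no baseline value, secondary endpoints are exploratory (Protocol 8.7.1.2.5), and biomarkers are not tested (SAP 4.6).

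Most of this stands, and it limits the point. It also rules out a stronger inference a reader might draw: that every evening Day -1 starter has a post-dose baseline, so that change from baseline is systematically understated. The documents do not support that. The fallback works whenever the waiver is used, and nothing shows that optional Day 1 tests are likely.

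What remains is that the operational wording can return a value its own principle forbids, and neither exception refers to the time of the first dose. The same-day exception could be stretched to cover this group only by treating the screening day as Day 1, which conflicts with displaying that dose as Screening.

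**Conclusion.** The concern holds as an ambiguity with limited reach: minor to moderate. Baseline **can** be post-dose for a patient first dosed on the evening of Day -1 who has an optional Day 1 value, or whose only early biomarker sample precedes the second dose rather than the first. Vital signs have a parallel gap through the relabelled Screening readings. PaO2/FiO2 is outside the general rule, and the primary analysis is untouched.

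The number of affected patients is unknown. The ACE2 percentages should not be read as an estimate of bias in this trial. They depend on an assumed affected share and on single-exponential decline, whereas Protocol 6.4 reports a bi-exponential decline in healthy volunteers. They also concern an untested marker. Protocol 8.4.5 gives a direction on drug for Ang II, Ang 1-7 and Ang 1-5 in the earlier ARDS study, but no size after one dose. For log-LDH and WHO improvement, no size of bias can be derived. The reason to act is that a covariate in the powered secondary analysis should be unambiguously pre-treatment, and making it so is cheap.

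**What to change.** In SAP section 4, replace the visit-label clause with: *the last non-missing value dated (and timed, where recorded) before the first IMP administration, whatever its visit label.* Then add:

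- If the first dose was given on Day -1, later values labelled Day 1 are post-baseline.
- Readings taken after a Day -1 dose and displayed as Screening are excluded from baseline, including for vital signs.
- If no pre-dose value exists, baseline is missing.
- A tie rule for untimed values on the first-dose date. A date alone cannot separate a Screening test from an evening dose on the same day. Scheduled Screening values, and Day 1 values for patients first dosed on Day 1, can count as pre-dose because Protocol 8.5.2.2 requires it. Readings from the relabelled unscheduled visit count only if marked as before dosing.

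Align the protocol's equation of baseline with Day 1, or list the departure in SAP section 5, and state that the WHO reference score uses this baseline. Settle the wording before unblinding and report how many patients were first dosed on Day -1.

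The cost is one paragraph and a comparison with the first dose, close to what the SAP already does by date for concomitant medication (4.2) and treatment-emergent events (4.5). The downside is that a few patients may lose a biomarker baseline.
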